10. PRIOR AND CONCOMITANT MEDICATION

World Health Organization-Drug Dictionary (WHODRUG) version March 2017 will be used to classify prior and concomitant medications by therapeutic class. Prior medication includes all treatments (including but not limited to prescription treatments, investigational products, vitamins, herbal treatments, and nondrug therapies) received within 30 days or 5 half-lives (whichever is longer) before the date of the first dose of investigational product and any procedures performed within 5 years before the date of the first dose of investigational product. Concomitant treatment refers to all treatment and ocular procedures received between the dates of the first dose of investigational product and the end of the follow-up period, inclusive.

Both prior and concomitant medication usage will be summarized by the number and proportion of subjects in each treatment group and overall by dosing regimen receiving each medication within each preferred term for the safety set. Medications can be counted both as prior and concomitant medication. Multiple medication usage by a subject in the same category will be counted only once. Ocular medications will be summarized for the study eye, the non-study eye, either eye if received in either eye, and both eyes if received in both eyes. For a medication to be counted for both eyes, the medication start date must be the same in both eyes for a given preferred term.

All prior and concomitant medication will be listed using the safety set.

11. SAFETY ANALYSES

The safety analysis will be performed using the Safety set. Safety and tolerability will be assessed by monitoring AEs, vital sign measurements, clinical laboratory test values, ECG readings, antidrug antibodies, drop comfort assessment, and ophthalmologic examinations. SDTP and MDTP outputs will be summarized separately. For SDTP, data will be summarized for two periods:

- a. Dosing period only: Day 1 SDTP – Day 2 SDTP
- b. Dosing period and washout period: Day 1 SDTP up to First Dose MDTP

For SDTP, ocular summaries will be presented for the study eye and the non-study eye. For MDTP, all ocular summaries will be presented for the study eye, the non-study eye, and for either eye. For summarization by either eye, the eye with the less favorable response at the given timepoint will be summarized which may result in different eyes being summarized at different visits. Adverse events and selected ocular assessments summaries will also be presented for both eyes. For summarization by both eyes, subjects with events or assessments occurring in both eyes will be included. In the MDTP, ocular summaries will be presented first by dose regimen then by dose level and placebo subjects will be pooled by dosing regimen. (eg, QD placebo subjects will be pooled together, BID placebo subjects will be pooled together, TID placebo subjects will be pooled together, and QID placebo subjects will be pooled together.) All subjects in the Safety set (including placebo-treated subjects) within a regimen will also be presented. (For example, all active QD doses and QD placebo patients will be combined for the QD dosing regimen summaries.)

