2. STUDY DESIGN

2.1 General Study Design

This is a multicenter, randomized, double-masked, placebo-controlled, single- and multiple-dose escalation study. Three different SHP639 concentrations will be studied: 0.1%, 0.3%, and 0.6%. There will be up to 12 cohorts in total, 1 cohort for each dose level and different dosing regimen. Each cohort will consist of 7 subjects for a total of 84 subjects in the study. Eligible subjects will be randomized in a 5:2 ratio to receive either SHP639 or placebo, respectively. The anticipated concentrations being studied for each dosing regimen are presented in the study schema in Figure 1.

A sufficient number of subjects will be screened and enrolled to ensure that at least 6 of 7 subjects complete each treatment in their assigned cohort. In the event that a sufficient number of subjects do not complete a cohort, replacement subjects may be enrolled. Each replacement subject will follow the same screening procedures and randomization sequence as the subject who is discontinued, regardless of when the subject discontinued.

Figure 1 Study Schema

Solid arrows are not drawn to scale and indicate both the flow of dosing regimens and the occurrence of a dose escalation meeting.

BID=twice daily; MDTP=multiple-dose treatment period; QD=once daily; QID=4 times daily; SD=single dose; SDTP=single-dose treatment period; TID=3 times daily

^a Dose escalation meetings will convene when 6 out of 7 subjects have completed Day 14 in the previous cohort's multiple-dose administration. This does not include the decision to move from Cohort B to C. Decisions will include safety, tolerability, and intraocular pressure data.

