2.3 Determination of Sample Size

A sufficient number of subjects will be screened to ensure the enrollment and completion of 84 subjects.

The number of subjects in this study is not based on statistical power considerations because the statistical analyses are primarily descriptive in nature. However, if at least 7 subjects complete each cohort, then there will be at least 65% to 85% probability of observing at least 1 occurrence of any AE with a true incidence rate for a given dose group of at least 15% to 25%, respectively.

It is estimated that dose escalation will occur for up to 3 dose levels (4 cohorts within each dose level). Each cohort will include 5 subjects randomized to active drug (SHP639) and 2 subjects randomized to placebo for an estimated total of at least 84 subjects.

For each cohort, the number of subjects will be increased as needed based on safety and IOP response to investigational product. Any cohort can be repeated to confirm findings with regard to safety or IOP response to investigational product.

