11.1 Adverse Events

Adverse events will be coded using the Medical Dictionary for Regulatory Activities (MedDRA). Ocular and non-ocular AEs will be summarized separately. Ocular summaries will be presented separately for the study eye, the non-study eye, either eye if the event occurred in either eye, and both eyes if the event occurred in both eyes. For an event to be counted for both eyes, the event start date must be the same in both eyes for a given preferred term.

The number of events, incidence, and percentage of treatment-emergent AEs (TEAE) will be calculated overall, by system organ class and preferred term by treatment group and overall by dosing regimen. AEs leading to drug withdrawal, Serious AEs (SAE), and AEs leading to death will be similarly summarized/listed. All information obtained on AEs will be displayed in a listing by treatment group, cohort, subject, treatment period (single dose or multiple dose; Cohort A only), visit, and day. A subject with multiple AEs within a body system will be counted only once. If more than 1 AE with the same preferred term is reported before the date of the first dose of double-blind investigational product, then the AE with the greatest severity will be used as the benchmark for comparison to the AEs occurring during the Double-blind Evaluation Phase under the preferred term.

Treatment-emergent AEs will be further summarized by severity and relationship to investigational product. An AE (classified by preferred term) that occurs during the Double-masked Evaluation Phase will be considered a TEAE if it has a start date and time on or after the date and time of first dose of double-blind investigational product or if it has a start date and time before the date and time of the first dose of double-blind investigational product, but increases in severity on or after the date and time of the first dose of double-blind investigational product. An AE that occurs more than 7 days after the date of the last dose of double-blind investigational product will not be counted as a TEAE.

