11.3 Vital Signs

Blood pressure, pulse rate and body temperature will be measured at the visits specified in Table 1; the time points during each visit are specified in Table 2, Table 3, Table 4, and Table 5 for Cohorts A, B, C, and D, respectively. Baseline for vital signs for SDTP is defined as the last non-missing scheduled assessment made prior to dosing in SDTP and baseline for MDTP is defined as the last non-missing scheduled assessment made prior to dosing in MDTP. Additional blood pressure and pulse rate measurements may be performed, as determined by the investigator, in order to ensure appropriate monitoring of subject safety and accurate recording of vital sign measurements. Any changes from baseline that are deemed clinically significant by the investigator are to be recorded as an AE.

Descriptive statistics for vital signs (systolic and diastolic blood pressure, pulse rate, and body weight) and their changes from baseline at each postbaseline visit and at the end of study will be presented by treatment group. Vital sign results will be listed by individual subject.

Vital sign values will be considered PCI if they meet both the observed value criteria and the change from baseline criteria listed in Table 7. The number and percentage of subjects with PCI postbaseline values will be tabulated by treatment group and overall by dosing regimen in the Safety set. Percentages will be calculated relative to the number of subjects with baseline and at least 1 postbaseline assessment. The numerator is the total number of subjects with at least 1 PCI postbaseline vital sign value. A supportive listing of subjects with postbaseline PCI values will be provided including the subject number, site, baseline, and postbaseline PCI values.

Table 7 Criteria for Potentially Clinically Important Vital Signs

Vital Sign Parameter	Flag	Criteria ^a	
		Observed Value	Change from Baseline
Systolic blood pressure (mmHg)	High	≥ 160	Increase of ≥ 20
	Low	≤ 90	Decrease of ≥ 20
Diastolic blood pressure (mmHg)	High	≥ 105	Increase of ≥ 15
	Low	≤ 50	Decrease of ≥ 15
Pulse rate (beats per minute)	High	≥ 100	Increase of ≥ 15
	Low	≤ 40	Decrease of ≥ 15
Weight (kg)	High	-	Increase of ≥ 7%
	Low	-	Decrease of ≥ 7%

^a A postbaseline value is considered as a PCI value if its meets both criteria for observed value and change from baseline.

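### The regimen-level safety column in the SAP mixes SHP639 and placebo subjects, and the SAP specifies no column that pools SHP639 subjects alone within a regimen

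*SAP*

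**What the plan says.** SAP Section 11 sets out three kinds of column for the multiple-dose period. The first two are dose levels within a regimen and placebo pooled within that regimen: "ocular summaries will be presented first by dose regimen then by dose level and placebo subjects will be pooled by dosing regimen". The third is a regimen total: "All subjects in the Safety set (including placebo-treated subjects) within a regimen will also be presented". The SAP's own illustration is explicit: "all active QD doses and QD placebo patients will be combined for the QD dosing regimen summaries".

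Later subsections call for an overall column by regimen. SAP 11.1 asks for treatment-emergent AEs "by system organ class and preferred term by treatment group and overall by dosing regimen", with serious AEs and AEs leading to withdrawal or death handled in the same way. SAP 11.3 says that PCI vital signs "will be tabulated by treatment group and overall by dosing regimen in the Safety set". SAP 11.4 uses the same layout for descriptive ECG statistics and PCI ECG values.

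No section of the SAP, and no title in its Section 16 output list, specifies a column of SHP639 subjects pooled across concentrations. SAP Section 1 places the table specifications in a separate document. Protocol 9.9.2 asks for AEs by dose and cohort with pooled placebo, and does not ask for an active-plus-placebo column.

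**The concern.** Safety and tolerability are the primary objective, and dosing frequency is one of the two axes of escalation. Each dose-level column is planned with only five SHP639 subjects per cohort, so a reader who wants to compare QD, BID, TID and QID will look to the regimen-level figure. As specified, two of every seven subjects behind that figure received no SHP639. The percentage shown is an average of the drug and placebo rates, weighted by the allocation ratio, and is not a rate on drug. When events are more frequent on drug than on placebo, it understates the drug rate. If placebo rates are similar across regimens, it also shrinks the differences between regimens.

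**Working it through.** **Inputs**

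- Allocation: "Eligible subjects will be randomized in a 5:2 ratio to receive either SHP639 or placebo, respectively" (SAP 2.1).
- Cohorts: "There will be up to 12 cohorts in total, 1 cohort for each dose level and different dosing regimen" (SAP 2.1), which is 3 concentrations × 4 regimens.
- Cohort make-up: "Each cohort will include 5 subjects randomized to active drug (SHP639) and 2 subjects randomized to placebo for an estimated total of at least 84" (SAP 2.3).
- Cohort D1 is not enrolled (Protocol 6.2.3.2, Table 10 footnote).
- Cohort B3 was repeated (SAP 13). The documents do not give the repeat's allocation, so 5:2 is an assumption.
- Replacements receive the treatment of the subject they replace (Protocol 6.2.2).

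**Reproducing the plan's figure.** 12 × (5 + 2) = 84, as stated: 60 active and 24 placebo. The active share is 60/84 = 5/7 = 0.714.

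**Active share by regimen**

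| Regimen | Active | Placebo | Combined | Active share |
|---|---|---|---|---|
| QD | 15 | 6 | 21 | 0.714 |
| BID, without the B3 repeat | 15 | 6 | 21 | 0.714 |
| BID, with the B3 repeat at 5:2 (assumed) | 20 | 8 | 28 | 0.714 |
| TID | 15 | 6 | 21 | 0.714 |
| QID, without D1 | 10 | 4 | 14 | 0.714 |

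**Formula.** With nA active subjects at rate pA and nP placebo subjects at rate pP:

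- combined rate = (nA·pA + nP·pP)/(nA + nP)
- combined rate − pP = [nA/(nA + nP)]·(pA − pP) = (5/7)·(pA − pP)

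So the excess over the regimen's own placebo is 5/7 of the active-only excess at any pair of rates. The raw rate is 5/7 of the active rate only if pP = 0.

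**Examples (rates assumed; 15 active, 6 placebo)**

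| On drug | On placebo | Combined column | Combined ÷ drug rate | Excess in column | Active-only excess |
|---|---|---|---|---|---|
| 40% | 0% | 28.6% | 0.71 | 28.6 points | 40 points |
| 40% | 10% | 31.4% | 0.79 | 21.4 points | 30 points |
| 40% | 20% | 34.3% | 0.86 | 14.3 points | 20 points |

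In counts, 6/15 on drug and 1/6 on placebo give 40.0% on drug and 7/21 = 33.3% combined. The excess over placebo is 33.3 − 16.7 = 16.7 points in the column (after rounding), against 40.0 − 16.7 = 23.3 points for drug alone. The ratio is 0.714.

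**Between regimens.** With the same placebo rate in two regimens, the placebo terms cancel. The difference between combined columns is then 5/7 of the difference between drug rates. Since the active share is the same in each regimen, the expected ordering is kept.

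**Sensitivity.** Replacements move the fraction a little. In a 21-subject regimen, one replaced active subject gives 16/22 = 0.727, and one replaced placebo subject gives 15/22 = 0.682.

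**The case against.** The strongest reply is that nothing is hidden. The combined group is presented in addition to the dose-level columns and the regimen's placebo. A reader can add up to three active columns, or subtract placebo from the total, and recover the all-active AE count. The analysis is descriptive, so no test depends on this column. This stands for counts and percentages. It does not stand for everything: SAP 11.4 applies the overall column to descriptive ECG statistics, SAP 15.1 includes the median, and a median cannot be rebuilt from the medians of separate columns.

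The reach of the column is also partly inferred. The defining sentence follows text on multiple-dose ocular summaries. Carrying it into SAP 11.1, 11.3 and 11.4 rests on the matching label and the QD illustration. Some outputs, such as TEAEs by severity and laboratory PCI values, are described by treatment group only. This limits the point to summaries that ask for the overall column.

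A reader might infer several stronger things that the documents do not support:

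- That displayed AE rates are 5/7 of the drug rates. This is true only when placebo has no events.
- That no active-only column will exist. The table shells are outside the SAP, so one can say only that the SAP does not specify it.
- That escalation decisions are distorted. The cohort stopping rule in Protocol 4.5.4 counts SHP639-treated subjects within a cohort, and no escalation rule uses this column.
- That an active-only column would make events likelier to be observed. That chance depends on how many subjects are dosed, and the combined column already contains all the regimen's active subjects.

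**Conclusion.** The point holds as a flaw in presentation. The only cross-concentration safety figure that the SAP specifies within a regimen combines drug and placebo, so it does not estimate risk on drug. Under planned allocation its excess over placebo is 5/7, about 71%, of the active-only excess in every regimen.

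This rests on three assumptions: the overall column in SAP 11.1, 11.3 and 11.4 has the definition given in SAP 11; allocation in the Safety set stays near 5:2; and the repeated B3 cohort, if counted, was also 5:2. The excess is measured against the regimen's own placebo, as SAP 11 pools it.

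The consequence is modest, since most of the information can be recovered from adjacent columns. The change is still worth making: it corrects the regimen-level result that readers see first, and supplies ECG medians that are otherwise unavailable.

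**What to change.** In the safety outcome summaries that use the overall column by regimen (TEAEs, PCI vital signs, ECG values and PCI ECG), add an *All SHP639* column for each regimen beside that regimen's pooled placebo. Planned sizes are 15 for QD and TID, 15 for BID (20 if the repeated B3 was also 5:2), and 10 for QID without D1. In the same summaries, drop the combined column or label it plainly as active plus placebo. Keep the combined total for disposition, demographics and medical history, where it describes who was studied.

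A further pool across regimens is not recommended. By the per-drop quantities in Protocol Table 9, it would span 35 µg once daily to 208 µg four times daily per eye, or 832/35 ≈ 24-fold, and would blur dose-response in its own way.

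The cost is a sentence in SAP 11 and changes to column headers and programming in the table shells. No new data are needed.

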11.1 Adverse Events

Adverse events will be coded using the Medical Dictionary for Regulatory Activities (MedDRA). Ocular and non-ocular AEs will be summarized separately. Ocular summaries will be presented separately for the study eye, the non-study eye, either eye if the event occurred in either eye, and both eyes if the event occurred in both eyes. For an event to be counted for both eyes, the event start date must be the same in both eyes for a given preferred term.

The number of events, incidence, and percentage of treatment-emergent AEs (TEAE) will be calculated overall, by system organ class and preferred term by treatment group and overall by dosing regimen. AEs leading to drug withdrawal, Serious AEs (SAE), and AEs leading to death will be similarly summarized/listed. All information obtained on AEs will be displayed in a listing by treatment group, cohort, subject, treatment period (single dose or multiple dose; Cohort A only), visit, and day. A subject with multiple AEs within a body system will be counted only once. If more than 1 AE with the same preferred term is reported before the date of the first dose of double-blind investigational product, then the AE with the greatest severity will be used as the benchmark for comparison to the AEs occurring during the Double-blind Evaluation Phase under the preferred term.

Treatment-emergent AEs will be further summarized by severity and relationship to investigational product. An AE (classified by preferred term) that occurs during the Double-masked Evaluation Phase will be considered a TEAE if it has a start date and time on or after the date and time of first dose of double-blind investigational product or if it has a start date and time before the date and time of the first dose of double-blind investigational product, but increases in severity on or after the date and time of the first dose of double-blind investigational product. An AE that occurs more than 7 days after the date of the last dose of double-blind investigational product will not be counted as a TEAE.

The overall number of subjects having any type of TEAEs will be summarized by treatment group. The number and percentage of subjects reporting TEAEs will be tabulated by system organ class (SOC) and preferred term (PT) by treatment group; TEAEs by severity will be tabulated by SOC, and maximum severity by treatment group. TEAEs considered related to investigational product will also be summarized by SOC and preferred term. If more than 1 AE occurs with the same PT for the same subject, then the subject will be counted only once for that PT using the most severe and most related occurrence for the summarization by severity and by relationship to investigational product. For both eyes summaries of related TEAEs, the events in both eyes must be considered related to investigational product. For both eyes summaries of TEAEs by severity, the events with same preferred term starting on the same date will be counted by the greater severity of the events in the two eyes (eg, the eyes will not be required to have same severity of the event to be counted.)

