7.1.3 Follow-up

A follow-up telephone call will take place 7 ± 2 days after the final dose (Day 28 of the MDTP). Site staff will query subjects for serious AEs (SAEs), AEs, and concomitant treatments. In the event that a subject is prematurely discontinued from the study, every attempt should be made to complete the follow-up assessments.

On Day 88 ± 4 days, subjects will attend the site for ADA blood sample collection. Site staff will query subjects for serious AEs (SAEs), and AEs. Adverse events that occur from Day 33 to Day 88 should be captured on the AE eCRF page. Concomitant medications during this period will also be captured. All AEs and SAEs that are not resolved at the time of this contact will be followed for an additional 30 days (see Section [8.1](#)).

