7.2 Study Evaluations and Procedures

7.2.1 Demographic and Other Baseline Characteristics

7.2.2 Safety

The name and address of each third-party vendor (eg, clinical laboratory) used in this study will be maintained in the investigator's and sponsor's files.

Actual safety assessment times will be monitored and recorded. The sponsor's expectation is that the investigator will ensure that every effort is made to perform all assessments at the precise protocol-scheduled time. Any safety assessment that deviates from the scheduled assessment time set forth in the protocol by more than ± 15 minutes will be considered a protocol deviation.

Ophthalmic assessments are considered safety assessments. If an ophthalmic assessment deviates from the scheduled assessment time set forth in the protocol by more than ± 15 minutes (or 5 minutes for the 15-minute and 30-minute time points), it will be considered a protocol deviation.

All AEs, prior medication use, and concomitant medication use will be assessed and monitored from the time the subject signs the ICF to completion of the study (including to time of screen failure or drop out/discontinuation); see Sections [7.2.2.4](#) and [8.1](#) for further details. The AEs will include nontreatment-emergent AEs (ie, those occurring from the time of informed consent

signature to the first dose of investigational product) and treatment-emergent AEs (ie, AEs occurring after the first dose). While housed at the site, subject safety will also be closely monitored through study procedures and physician oversight.

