7.2.2.4 Adverse Event Collection

At each study visit, subjects will be questioned in a general way to ascertain if AEs have occurred since the previous visit (eg, "Have you had any health problems since your last visit?"). Adverse events are collected from the time informed consent is signed until Day 88/FU (refer to [Section 8](#)). Adverse events that occur after Day 33 to Day 88/FU should be captured on the AE eCRF page.

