8.2.4 Serious Adverse Event Collection Time Frame

All SAEs (regardless of relationship to study) are collected from the time the subject signs the informed consent until the defined follow-up period stated in Section 7.1.3 and must be reported to the Shire Global Drug Safety Department and the CRO/Shire medical monitor within 24 hours of the first awareness of the event.

In addition, any SAE(s) considered “related” to the investigational product and discovered by the investigator at any interval after the study has completed must be reported to the Shire Global Drug Safety Department within 24 hours of the first awareness of the event.

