9.4 Statistical Analysis Process

The study will be analyzed by the sponsor or its agent.

The statistical analysis plan (SAP) will provide the statistical methods and definitions for the analysis of the PK, PD, and safety data, as well as describe the approaches to be taken for summarizing other study information such as subject disposition, demographics and baseline characteristics, investigational product exposure, and prior and concomitant medications. The SAP will also include a description of how missing, unused and spurious data will be addressed.

To preserve the integrity of the statistical analysis and study conclusions, the SAP will be finalized before database lock.

All statistical analyses will be performed using SAS[®] software (SAS Institute, Inc, Cary, NC 27513).

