9.9.2 Statistical Analysis of Safety Data

The placebo subjects will be pooled together as a pooled placebo group.

All vital sign, clinical laboratory, ECG, ADA, drop comfort assessment, and ophthalmologic examination data (per schedule of events) will be listed by dose, cohort, subject, treatment period (single dose or multiple dose; Cohort A only), visit, day, and time point (for days with multiple assessments per day). If the ranges are available then abnormalities will be flagged. Summary statistics with number of subjects, mean, SD, median, minimum, and maximum will be provided by dose, cohort, treatment period (single dose or multiple dose; Cohort A only), visit, day, and time point (for days with multiple assessments per day).

Adverse events will be coded using the Medical Dictionary for Regulatory Activities. The number of events, incidence, and percentage of treatment-emergent AEs will be calculated overall and by system organ class and preferred term by dose and cohort. Treatment-emergent AEs will be further summarized by severity and relationship to investigational product. Adverse events related to investigational product, AEs leading to withdrawal, SAEs, and deaths will be similarly summarized/listed. All information obtained on AEs will be displayed by dose, cohort, subject, treatment period (single dose or multiple dose; Cohort A only), visit, and day. A subject with multiple AEs within a body system will be counted only once.

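### SAP 11.1 stops counting treatment-emergent AEs 7 days after last dose, narrower than Protocol 7.2.2, and no table covers AEs, SAEs or fatal AEs with later onset

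*SAP*

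**What the plan says.** **Protocol, definition.** Section 7.2.2 divides AEs into those between consent and first dose and "treatment-emergent AEs (ie, AEs occurring after the first dose"). Nothing after that bracket sets an end.

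**Protocol, collection.** Section 7.2.2.4: "Adverse events are collected from the time informed consent is signed until Day 88/FU". Section 7.1.3: "Adverse events that occur from Day 33 to Day 88 should be captured on the AE eCRF page". Section 8.2.4: "All SAEs (regardless of relationship to study) are collected from the time the subject signs the informed consent until the defined follow-up period", with a reference back to 7.1.3.

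**Protocol, analysis.** Section 9.9.2 plans counts, incidence and percentages of treatment-emergent AEs by system organ class and preferred term, then by severity and relationship. It adds: "Adverse events related to investigational product, AEs leading to withdrawal, SAEs, and deaths will be similarly summarized/listed". Section 9.4 says that the SAP "will provide the statistical methods and definitions for the analysis of the PK, PD, and safety data".

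**SAP.** Section 11.1 adds the upper limit: any event which "occurs more than 7 days after the date of the last dose of double-blind investigational product will not be counted as a TEAE". It also plans a listing of all AE information. Section 16 names the AE tables, each titled treatment-emergent. The AE, SAE, withdrawal and death listings (16.2.7.1, 16.2.7.2, 16.2.7.3, 16.2.7.5) carry no such restriction in their titles.

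**The concern.** Safety and tolerability are the primary objective of this first-in-human study, and the AE tables are its main summary. The protocol deliberately collects events to Day 88; Appendix 1 records AE collection at that visit as an addition in Amendment 2, and the SAP is written against the later Amendment 3. A reader who takes the protocol's description of treatment-emergent AEs to the SAP tables will assume that they run to the end of follow-up. They stop at Day 35 in a completer, and earlier in a subject who stops dosing early.

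A listing shows each late event but gives no incidence by treatment group and no comparison with pooled placebo. As a hypothetical illustration, one subject with a late SAE among the 5 active subjects of a cohort would be 1/5 in a table following Protocol 7.2.2 and is 0/5 in the table that SAP 11.1 produces.

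**Working it through.** **Inputs**

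- Last dose in a completer: Day 28 of the MDTP (Protocol 6.2.3.1).
- Final visit: 60 days after last dose, labelled Day 88 (Protocol Table 1 footnotes), with a window of ±4 days (Protocol 7.1.3).
- End of counting: 7 days after last dose (SAP 11.1). I read an AE's occurrence as its onset.

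**The plan's own figure.** 28 + 60 = 88, which agrees with the stated Day 88.

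**Days outside the rule**

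- Last countable onset day: 28 + 7 = Day 35. First excluded day: Day 36.
- Days after last dose, to Day 88: 88 − 28 = 60.
- Excluded days: 88 − 35 = 53. Share: 53/60 = 88.3%.
- Visit on Day 84: (84 − 35)/(84 − 28) = 49/56 = 87.5%.
- Visit on Day 92: (92 − 35)/(92 − 28) = 57/64 = 89.1%.
- Under the Protocol 7.2.2 description, no day after first dose is excluded.

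**AE tables in SAP Section 16**

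| Group | Table numbers | SDTP dosing | SDTP dosing and washout | MDTP | Total |
|---|---|---|---|---|---|
| Overall | 14.3.1.1.x | 1 | 1 | 1 | 3 |
| By class and term | 14.3.1.2.x | 2 | 2 | 2 | 6 |
| By severity | 14.3.2.1.x | 2 | 2 | 2 | 6 |
| Related | 14.3.2.2.x | 2 | 2 | 2 | 6 |
| Leading to death | 14.3.3.1.x | 2 | 2 | 2 | 6 |
| Leading to withdrawal | 14.3.3.2.x | 2 | 2 | 2 | 6 |
| Serious | 14.3.3.4.x | 2 | 2 | 2 | 6 |
| All | | 13 | 13 | 13 | 39 |

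**Can a late event reach any of them?** By SAP 11, the 13 SDTP dosing tables end at SDTP Day 2, and the 13 dosing and washout tables end at the first MDTP dose. Neither set reaches the follow-up. The 13 MDTP tables are restricted to treatment-emergent AEs, so the 7-day rule removes later onsets. That leaves 0 of 39 tables for an AE, SAE or fatal AE with onset on Days 36 to 88.

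**Does SAP 15.4.3 fill the gap?** It sends AEs that start on or after the first MDTP dose to the MDTP outputs and gives no end date. But it is a rule for AEs with missing times, and the outputs that it points to are the same treatment-emergent tables.

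**The case against.** The strongest reply is that no protocol requirement is broken. Protocol 9.4 leaves safety definitions to the SAP. Protocol 7.2.2 is a monitoring paragraph whose purpose is to separate events before and after first dose. Section 9.9.2 sets no end date for treatment-emergent AEs, and its wording on related AEs, withdrawals, SAEs and deaths can be met by a listing. SAP 11.1 states its rule openly. In a descriptive study with 7 subjects per cohort, a listing by subject shows a late SAE or death in full.

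The documents also contain grounds for a short window, although the SAP does not cite them. Systemic exposure after topical dosing in animals was very low or undetectable (Protocol 1.2.1). The follow-up call falls about a week after dosing ends. Usual medication may be resumed after Day 29 discharge (Protocol 5.2.2), which confounds later events.

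Most of this stands, and it rules out several stronger readings that a reader might infer:

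- *The SAP violates the protocol.* It does not; a bounded window is within the SAP's remit.
- *Late events are lost.* They are not; they are collected and listed.
- *The tables miss 88% of events.* The figure counts days, and no event rate is given.
- *The SAP contradicts itself because concomitant treatment is counted* "between the dates of the first dose of investigational product and the end of the follow-up period, inclusive". That period repeats Protocol 5.2, and medication and AE tables need not share a window.

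The reply does not answer one thing. The incidence that Protocol 9.9.2 asks for, read with 7.2.2, differs from the incidence under SAP 11.1. The SAP does not say so, and no table shows the difference.

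**Conclusion.** The point holds as a gap in declaration and tabulation, and should be fixed. In a completer, AEs, SAEs and fatal AEs with onset on Days 36 to 88 (53 of 60 post-dose days) enter none of the 39 AE tables and appear only in listings. The effect on the reported safety profile cannot be sized, because the documents give no late-event rate; it may be nil if no late events occur.

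This rests on four assumptions:

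- The 7-day rule applies to onset, so a fatal AE that begins by Day 35 is still tabulated even if death comes later.
- The tables follow their titles and the SAP 11.1 text; the detailed specifications are in a separate document that was not available.
- No statement about the narrower window stands in the SAP front pages, which were also not available.
- Day 88 is nominal, with an actual visit between Day 84 and Day 92.

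**What to change.** 1. Keep the 7-day window if wanted. State in SAP 11.1 that it is an on-treatment definition, narrower than the description in Protocol 7.2.2, and give the reason.
2. Add MDTP summary tables of all AEs, related AEs, SAEs and AEs leading to death, with onset from first MDTP dose through the Day 88 follow-up visit. Put onset within 7 days of last dose and onset beyond it in separate columns.
3. State that these tables are produced once Day 88 data are complete. Protocol 9.5 and SAP 13 trigger the final unmasked analysis at Day 29, which precedes both the end of follow-up and, for the last subjects, Day 35.

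The cost is a short addition to the SAP text, one onset-period flag and a few tables from data already collected. The added tables must wait for Day 88 data. Late events may be confounded by medication resumed after Day 29; the separate columns keep them apart from on-treatment events.
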